### **3 OBJECTIVES AND ENDPOINTS**

#### ***3.1 Primary Objective***

- To assess the antitumor activity of PM01183 in terms of ORR, according to RECIST v1.1, in each Cohort of MBC patients.

#### ***3.2 Secondary Objectives***

- To further characterize the antitumor activity of PM01183 in terms of duration of response (DR), clinical benefit [ORR or stable disease lasting over three months (SD  $> 3$  months)], PFS, and one-year overall survival (1y-OS).
- To evaluate whether the presence of a known germline mutation in BRCA1/2 predicts response to PM01183 in MBC patients.
- To explore the activity of PM01183 in specific breast cancer subpopulations according to hormonal receptor status, HER-2 overexpression, number and/or type of prior therapies, or according to other available histological/molecular classifications.
- To evaluate the safety profile of this PM01183 administration schedule (Day 1, q3wk) in this patient population.
- To analyze the pharmacokinetics (PK) of PM01183 in this patient population.
- To explore PK/PD (pharmacokinetic / pharmacodynamic) correlations, if applicable.
- To evaluate the pharmacogenomic (PGx) expression profile of selected putative markers potentially predictive of response to PM01183, in tissues from archived tumor samples.

#### ***3.3 Endpoints***

##### **Primary endpoint:**

- Overall response rate (ORR) in the population evaluable for efficacy, according to RECIST v1.1.

##### **Secondary endpoints:**

- Duration of response (DR).

- Clinical benefit, defined as the percentage of patients with ORR or SD > 3 months, according to RECIST v1.1.
- Progression-free survival (PFS).
- Overall survival rate at one year (1y-OS).
- Treatment safety: AEs, serious AEs (SAEs) and laboratory abnormalities will be graded according to the NCI-CTCAE (v4).
- PK analysis and PK/PD correlation, if applicable.
- PGx expression profile, in tissues from archived tumor samples.

## 4 PATIENTS EVALUABILITY CRITERIA

The study population will include patients with MBC histologically proven.

Analysis sets definitions:

- “All Included Patients” analysis set is defined as all patients recorded in the database who are included in the trial, independently of whether they have received the study drug or not.
- “All Treated Patients” analysis set is defined as all included patients who have received at least part of one infusion of PM01183.
- “All Evaluable Patients” analysis set is defined as all eligible patients who have at least one complete infusion of PM01183, and either have at least one assessment (as per RECIST v1.1) or have been categorized as “treatment failures”. Patients who discontinue treatment due to any treatment-related toxicity before an appropriate tumor assessment has been performed or those withdrawn after more than two weeks on treatment without any formal evaluation will be defined as “treatment failures”. These patients will be included as inevaluable for response in the analysis of objective response as per RECIST v1.1, although they will not need to be replaced as they will be considered evaluable for efficacy.
- “All Responder Patients” analysis set is defined as all evaluable patients who have had CR or PR as overall best response according to the RECIST v1.1 criteria.

### 4.1 *Included Population*

The “All Included Patients” data set will be used for the descriptive analysis of baseline characteristics.

### 4.2 *Efficacy Populations*

The “All Evaluable Patients” analysis set will be used for the primary endpoint analysis of ORR and for the secondary endpoints of PFS, 1y-OS and clinical benefit rate.

The “All Responder Patients” set will be used for the secondary endpoint analysis of DR.

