6.10. REPLACEMENT OF PATIENTS

Patients will be replaced if they are not evaluable for the primary endpoint of the study (ORR as per RECIST v1.1), specifically (any of the following):

- They are not eligible.
- They have not been treated or have not completed at least one PM01183 infusion.
- They are not evaluable for ORR as per RECIST v1.1 and they are not categorized as "treatment failures". Treatment failures will not be replaced and are defined as patients who:
 - Discontinue treatment due to any treatment-related toxicity before an appropriate tumor assessment has been performed, or
 - Withdraw PM01183 after more than two weeks on treatment without any formal evaluation

All replaced patients will be included in the general safety analysis, if appropriate.

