7. STUDY EVALUATIONS

7.1. EFFICACY

For patients to be evaluable for efficacy they must be eligible, have at least one complete infusion of PM01183, and either have at least one assessment (as per RECIST v1.1) or be categorized as “treatment failure”.

Antitumor activity will be assessed using RECIST v1.1, on a set of measurable lesions identified at baseline as target lesions and non-target lesions (if any) identified at baseline as non-target lesions and followed until PD by an appropriate method (contrast enhanced helical CT-scan, MRI, and/or clinical assessment).

Radiological and/or clinical (whenever appropriate) tumor assessment will be performed at baseline and every six weeks (two cycles) until Cycle 6 or evidence of PD. After Cycle 6, tumor assessment will be performed every nine weeks (three cycles) until evidence of PD. If an objective response is observed, according to RECIST v1.1, it must be confirmed by the same method at least four weeks after the date of the first documentation of response.

The date of response, the date of clinical or radiological PD, and the date of death will be registered and documented as appropriate.

A copy of the imaging tests conducted on the patients during this clinical trial may be requested by the Sponsor for evaluation. In addition, an independent radiological review committee may be set up, upon Sponsors' request, to review tumor assessment performed for all responding patients (partial or complete response) after study completion.

Patients will be categorized as “treatment failures” if they:

- Discontinue treatment due to any treatment-related toxicity before an appropriate tumor assessment has been performed, or
- Withdraw PM01183 after more than two weeks on treatment without any formal evaluation.

These data will be included as non-evaluable (NE) in the analysis of objective response as per RECIST v1.1, although these patients will not need to be replaced as they will be considered evaluable for efficacy.

BRCA1/2 germline mutation analysis

In patients included in Cohort B who respond to PM01183 treatment and whose BRCA 1/2 mutation status is unknown at study entry, an analysis will be performed in order to confirm or exclude deleterious germline BRCA 1/2 mutation. To this end, a blood sample will be collected at the time of response. If a BRCA 1/2 mutation is found in her sample then the patient will be analyzed along with patients included in Cohort A.

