8.1.2. Secondary Endpoints

- Duration of response (DR), defined as the time between the date when the response criteria (PR or CR, whichever is first reached) are fulfilled to the first date when PD, recurrence or death is documented.
- Clinical benefit, defined as the percentage of patients with ORR or SD > 3 months, according to RECIST v1.1.
- Progression-free survival (PFS), defined as the period of time from the date of first infusion to the date of PD, death (due to any cause), or last tumor evaluation.
- Overall survival rate at one year (1y-OS), defined as the Kaplan-Meier estimate of the probability of patients to remain alive at one year. Overall survival (OS) will be defined as time from the date of first infusion to the date of death or last contact
- Treatment safety: AEs, SAEs, and laboratory abnormalities will be graded according to the NCI-CTCAE (v4), reasons for treatment discontinuation, dose reduction and/or treatment delays.
- PK descriptive analysis and PK/PD correlation, if applicable.
- PGx expression profile of selected putative markers potentially predictive of response to PM01183, in tissues from tumor samples.

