#### Secondary endpoint

The following time-related parameters would be analyzed according to available follow-up data:

**Duration of response (DR)** is defined as time from first observation of response to the date of disease progression, recurrence or death. Other causes will be censored. Although the responses have to be confirmed according to RECIST v1.1 criteria, the first documentation, not the confirmation, will be taken into account to calculate DR. Patients who progress or die will be considered to have had an event, except if this event occurs after the start of subsequent antitumor therapy, in which case the patient will be censored at the time of last disease assessment prior to or on the first day of the first subsequent antitumor therapy.

**Clinical benefit rate** is calculated as the number of patients who have had CR or PR or SD  $\geq 3$  months as overall best response according to the RECIST v1.1 criteria, divided by the number of patients in the “All Evaluable Patients” analysis set.

**Progression-free survival (PFS)** is defined as the time from start of treatment to the date of documented progressive disease (PD) by RECIST v1.1 criteria or death (regardless of the cause of death), whichever comes first. Patients who progress or die will be considered to have had an event, except if this event occurs after the start of subsequent antitumor therapy, in which case the patient will be censored at the time of last disease assessment prior to or on the first day of the first subsequent antitumor therapy. If the patient is lost for the assessment of progression during the follow-up period, or has more than one missing follow-up between the date of last tumor assessment and the date of progression, death or further antitumor therapy, the PFS will be censored at the date of last valid disease assessment before the missing evaluations.

**Overall survival (OS)** is defined as the time from the date of start of treatment to the date of death or last contact. **1 year overall survival (1y-OS)** is defined as the Kaplan-Meier estimate of the probability of patients alive after 12 months from the date of start of treatment.

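### PFS, 1y-OS, ORR and clinical benefit are estimated only in All Evaluable Patients: some eligible treated patients enter no efficacy estimate, and the two-week boundary of that set is undefined

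*SAP*

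**What the plan says.** SAP 4.2 assigns four endpoints to one set, All Evaluable Patients. It says that this "analysis set will be used for the primary endpoint analysis of ORR and for the secondary endpoints of PFS, 1y-OS and clinical benefit rate". SAP 11.3 applies the same set to all efficacy tables.

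Protocol 7.1 gives the entry conditions: "For patients to be evaluable for efficacy they must be eligible, have at least one complete infusion of PM01183", plus either a RECIST assessment or treatment-failure status. SAP 4 matches it. There are two routes to treatment failure. One is stopping for treatment-related toxicity before an assessment. The other is time on treatment: "those withdrawn after more than two weeks on treatment without any formal evaluation will be defined as" treatment failures.

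Protocol 6.10 replaces patients outside the set, including this category: "They have not been treated or have not completed at least one PM01183 infusion". It then says: "All replaced patients will be included in the general safety analysis, if appropriate". The wider All Treated Patients set (at least part of one infusion) is used for safety only (SAP 4.3, 7 and 12).

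PFS and OS run from the start of treatment and need no scan to record a death. The PFS event in SAP 6.1 is documented progression "or death (regardless of the cause of death), whichever comes first".

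**The concern.** Requiring an assessment, or a defined failure, has some logic for a response rate. It has little for PFS or OS, where a death is an event whether or not the tumor was re-imaged. Here membership of the set depends on what happens after the first infusion, and some of the patients it removes may be the earliest deaths. A single-arm trial has no comparator in which a similar loss could offset this.

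The protocol's own RECIST summary (Appendix 2, 2.8.1) advises that conclusions rest on all eligible or all treated patients, not on a selected evaluable subset. The inevaluable row of SAP Table 11.3.1.1 does not fill the gap, because its footnote limits it to treatment failures, who are already in the set.

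**Working it through.** **Who is in and who is out (eligible, treated patients).**

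| Patient | In All Evaluable? | Basis |
|---|---|---|
| Complete infusion, stops unscanned for treatment-related toxicity | In | Toxicity route |
| First infusion partial, a later one complete, then scanned | In | Infusion condition met |
| Never completes an infusion, even if toxicity stopped it | Out | Infusion condition fails |
| Complete infusion, dies or starts new antitumor therapy unscanned within two weeks, not for treatment-related toxicity | Out | Neither route applies |
| Complete infusion, stops unscanned within two weeks for another reason, alive, no new therapy | Unclear | Depends on the clock |

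The last two rows turn on how long a patient counts as on treatment. Protocol 6.2 runs the on-treatment period from first infusion to end of treatment, which is 30 days after the last dose unless death or new antitumor therapy comes first; SAP 8.4 agrees. A patient who dies on day 10 therefore has 10 days on treatment and fails the two-week criterion on any reading. A patient who stops on day 10, alive and without new therapy, has more than two weeks under that definition and could be a treatment failure. If the clock stops at the decision to withdraw, she is out.

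**Would the PFS censoring rule remove these deaths anyway?** No. SAP 6.1 censors when there is "more than one missing follow-up between the date of last tumor assessment and the date of progression, death" or further therapy. The first scheduled scan is at six weeks, with a 14-day window, so a death by day 14 has missed none. Only the choice of set removes it. Patients who start new therapy unscanned would be censored for PFS at baseline and barely affect it; OS has no such censoring.

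**The plan's own figures.** The critical count is n·p0 + 1.96·√(n·p0·(1−p0)).
- Cohort A: 10.6 + 1.96 × 2.912 = 16.31, so 17 of 53, as stated.
- Cohort B: 6.4 + 1.96 × 2.4 = 11.10, so 12 of 64, as stated.
- Cohort A1: 4/20 has an exact 95% lower limit of 5.73%, above 5% as stated.

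**Effect on 1y-OS.** The documents give neither an expected 1y-OS nor the number excluded. I assume S = 40% to 70% and e = 1 to 3 restored patients. If all e die before any other event or censoring, the estimate becomes S·n/(n+e), a fall of S·e/(n+e), in percentage points:

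| n | e = 1 | e = 2 | e = 3 |
|---|---|---|---|
| 53 | 0.7–1.3 | 1.5–2.5 | 2.1–3.8 |
| 64 | 0.6–1.1 | 1.2–2.1 | 1.8–3.1 |
| 20 | 1.9–3.3 | 3.6–6.4 | 5.2–9.1 |

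For example, with n = 53, S = 0.70 and e = 3: 0.70 × 53/56 = 0.6625, a fall of 3.75 points.

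If instead the restored patients are alive at one year, with no earlier censoring, the estimate rises by (1−S)·e/(n+e). With e = 1 and n = 53 this is 0.60/54 = 1.1 points at S = 40% and 0.30/54 = 0.6 points at S = 70%.

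**Effect on ORR,** at the minimum passing counts, adding 1 to 3 non-responders:
- 17/53 = 32.1% becomes 17/54 = 31.5% to 17/56 = 30.4%.
- 12/64 = 18.8% becomes 12/65 = 18.5% to 12/67 = 17.9%.
- 4/20 = 20.0% becomes 4/21 = 19.0% to 4/23 = 17.4%.

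**The case against.** The strongest reply has four parts.

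- **The gap is narrow.** Toxicity stops after a complete infusion are kept. Entry requires ECOG 0 or 1, albumin of at least 3 g/dl and adequate organ function, so non-toxic death within two weeks should be uncommon. This stands, and it is why the effect is probably small.
- **The patients are not hidden.** SAP Table 10.1.1 gives eligible, treated and evaluable counts. Listings 10.1.4 and 16.2.3 identify the exclusions, and 12.3.2.2 gives the deaths with dates. This also stands. What is missing is an estimate that includes these patients.
- **The set is pre-specified.** Protocol 8.1.1 fixes the evaluable population for ORR, and PFS and 1y-OS are secondary estimates, without a threshold, in a trial that calls itself exploratory. That justifies leaving the primary analysis alone. It is no reason to omit a supportive analysis.
- **The direction for survival is not settled.** A patient whose only infusion was interrupted, or who moved to new therapy, may live beyond a year. This is correct.

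A reader might infer that every patient who leaves unscanned within two weeks is lost. The on-treatment definition does not support that for those who leave alive and without new therapy. A reader might also infer that PFS and OS must be inflated; that follows only if the excluded patients die early.

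**Conclusion.** The point holds as a minor one. Two groups of eligible treated patients are in no planned efficacy estimate: those who never complete an infusion, and those who die or start new antitumor therapy unscanned within two weeks for a reason other than treatment-related toxicity. A third group, stopping in that window unscanned, alive and without new therapy, cannot be classified from the text.

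For ORR and clinical benefit the exclusions can only raise the estimate, taking it that nobody qualifies as a responder or as durable stable disease on less than one full infusion. For PFS and 1y-OS the direction depends on the excluded patients' survival. The size cannot be derived from the documents; the ranges shown rest on assumed counts and an assumed 1y-OS. They use the planned cohort sizes, although the roughly 110 evaluable patients expected are fewer than 53 + 20 + 64 = 137; in a smaller cohort each restored patient weighs more.

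It would be tempting to say that the trial's conclusions are at risk. At the exact boundary three restored patients matter: 17/56 gives z = (0.3036 − 0.20)/√(0.16/56) = 1.94, below 1.96, and 4/23 has a lower limit of 4.95%, below 5%. In Cohort B it takes seven (12/71, z = 1.94). One responder above the Cohort A boundary, it already takes seven (18/60, z = 1.94). The formal rules are defined on the evaluable set and nothing here overturns them.

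**What to change.** 1. In SAP 4.2 and 11.3, add supportive analyses of PFS, 1y-OS, ORR and clinical benefit in all eligible patients who received at least part of one infusion. The existing All Treated Patients set would also serve, but it brings in ineligible treated patients as well. Count deaths as events under the existing PFS and OS rules and unassessed patients as non-responders. Report the results beside the evaluable-set results.
2. In SAP 4, state whether the two-week criterion uses the on-treatment definition of protocol 6.2 or the time to the withdrawal decision.
3. Keep the evaluable-set ORR and the 17/53, 4/20 and 12/64 rules as the only formal decision rules. If the two sets differ, those rules decide and the report states the difference.

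The cost is a SAP edit and a second run of five existing tables (11.3.1.1, 11.3.1.2, 11.3.2.2, 11.3.2.3 and 11.3.2.4). As supportive results they are compatible with protocol 7.1 and 8.1.1. The downside is a second estimate per endpoint to explain, possibly slightly lower.

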#### **4.3 Safety Population**

The safety analysis for the secondary endpoint will be based on the “All Treated Patients” analysis set.

### **5 SAMPLE CONSIDERATIONS**

#### **5.1 Sample Size**

The primary endpoint for this phase II study is to evaluate ORR.

- **Cohort A (BRCA+):**

At least 53 evaluable patients will be recruited to test the null hypothesis that ORR is 20% or less ( $p \leq 0.20$ ) vs. the alternative hypothesis that 40% or more patients have objective response ( $p \geq 0.4$ ). With these assumptions, if the number of evaluable patients with objective response is  $\geq 17$ , then this would allow the rejection of the null hypothesis.

- **Cohort A1 (BRCA+/PARPi):**

At least 20 evaluable patients will be recruited for an exploratory analysis: if the number of patients responding is  $\geq 4$  (20%), the lower limit of the exact binomial 95% confidence interval will be higher than 5% and thus lack of activity in this subpopulation will be ruled out.

- **Cohort B (unselected):**

At least 64 evaluable patients will be recruited to test the null hypothesis that ORR is 10% or less ( $p \leq 0.10$ ) vs. the alternative hypothesis that 25% or more patients have objective response ( $p \geq 0.25$ ). With these assumptions, if the number of evaluable patients with objective response is  $\geq 12$ , then this would allow the rejection of the null hypothesis.

The variance of the standardized tests is based on the null hypothesis. The type I error (alpha) associated with this one-sided test is 0.025 and the type II error (beta) is  $<0.1$ ; hence, statistical power is  $> 90\%$ .

Futility analysis controlled by the Gamma family boundary will be performed when 20 and 30 patients have been evaluated in Cohorts A [Gm(-2)] and B [Gm(-1.5)], respectively. If less than four out of 20 patients in Cohort A, or less than three patients out of 30 in Cohort B achieve an objective response, recruitment to that Cohort will be stopped. About 110 evaluable patients are finally expected to be included in the three Cohorts: Cohort A (BRCA+), Cohort A1 (BRCA+/PARPi), and Cohort B (unselected).

### **6 STATISTICAL METHODOLOGY FOR EFFICACY**

Frequency tables will be performed for categorical variables, whereas continuous variables will be described by means of summary tables that will include the median, minimum, and maximum of each variable.

#### **6.1 Planned Analysis and Definitions**

##### **Primary endpoint**

The primary study analysis will be based on the ORR in the “All Evaluable Patients” analysis set.

**Overall response rate (ORR)** is calculated as the number of patients who have had CR or PR as overall best response according to the RECIST v1.1 criteria, divided by the number of patients in the “All Evaluable Patients” analysis set.

#### Secondary endpoint

The following time-related parameters would be analyzed according to available follow-up data:

**Duration of response (DR)** is defined as time from first observation of response to the date of disease progression, recurrence or death. Other causes will be censored. Although the responses have to be confirmed according to RECIST v1.1 criteria, the first documentation, not the confirmation, will be taken into account to calculate DR. Patients who progress or die will be considered to have had an event, except if this event occurs after the start of subsequent antitumor therapy, in which case the patient will be censored at the time of last disease assessment prior to or on the first day of the first subsequent antitumor therapy.

**Clinical benefit rate** is calculated as the number of patients who have had CR or PR or SD  $\geq 3$  months as overall best response according to the RECIST v1.1 criteria, divided by the number of patients in the “All Evaluable Patients” analysis set.

**Progression-free survival (PFS)** is defined as the time from start of treatment to the date of documented progressive disease (PD) by RECIST v1.1 criteria or death (regardless of the cause of death), whichever comes first. Patients who progress or die will be considered to have had an event, except if this event occurs after the start of subsequent antitumor therapy, in which case the patient will be censored at the time of last disease assessment prior to or on the first day of the first subsequent antitumor therapy. If the patient is lost for the assessment of progression during the follow-up period, or has more than one missing follow-up between the date of last tumor assessment and the date of progression, death or further antitumor therapy, the PFS will be censored at the date of last valid disease assessment before the missing evaluations.

**Overall survival (OS)** is defined as the time from the date of start of treatment to the date of death or last contact. **1 year overall survival (1y-OS)** is defined as the Kaplan-Meier estimate of the probability of patients alive after 12 months from the date of start of treatment.

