6.7. EVALUATIONS AT END OF TREATMENT

The EOT visit will be scheduled at 30 days after the last dose of study treatment (a window of \pm 7 days is allowed), unless the patient starts a new antitumor therapy or dies within those 30 days from the last dose, in which case the date of administration of this new antitumor therapy or the date of death will be considered as EOT.

For treated patients, regardless of the reason for discontinuation, if no recent data are available (i.e., within last 10 days prior to the EOT visit) or if the last data available show a grade ≥ 2 alteration, the following work-up will have to be done at this EOT visit:

- Complete physical examination, including weight (height only at baseline).
- ECOG performance status.
- Vital signs (heart rate, blood pressure, body temperature).
- Coagulation panel.
- Hematology.
- Biochemistry A.
- Biochemistry B.
- Pregnancy test, if clinically indicated.
- Electrocardiogram (ECG), if clinically indicated.
- LVEF by echocardiography (ECHO) or MUGA, if clinically indicated.
- Radiological and/or clinical tumor assessment (if not previously done and if the reason for treatment discontinuation was other than PD).
- Intercurrent events, concomitant diseases and treatments.
- Safety assessment (AEs).

Adverse events (AEs) and serious adverse events (SAEs) must be reported until 30 days after the last PM01183 administration (for safety reporting see Section [11.2](#)).

The Sponsors will evaluate all safety information that is spontaneously reported by an Investigator beyond the time frame specified in the protocol.

Patients of childbearing potential who use adequate contraception methods while on study should be reminded to continue adequate contraception for a period of six weeks after last study drug administration.

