6.8. FOLLOW-UP AFTER END-OF-TREATMENT VISIT

The date and reason of the end of study will be recorded on the patient's CRF.

After the end of treatment, all AEs and SAEs suspected to be related to PM01183 must be followed-up until recovery to grade ≤ 1 or symptoms stabilization whenever possible (for safety reporting see Section [11.2](#)). Pregnancy and suspected pregnancy occurring within six weeks from the patient's last PM01183 administration are considered immediately reportable events.

Additionally, radiological and/or clinical tumor assessments will be done during the follow-up only to those patients who discontinue treatment without documented disease progression. Patients will be followed every two months during the first six months after last tumor assessment and every three months thereafter until PD, start of other antitumor therapy, death, or study completion (clinical cut-off), whichever occurs first.

After documented progression or start of a new antitumor therapy, patients will be followed every six months, until death or study completion (clinical cut-off), whichever occurs first. For this purpose of collecting information on the patient's survival exclusively, a documented telephone call would be acceptable and no visits to the hospital will be required.

Patients who withdraw consent will not be followed with any study procedures.

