2.4.2 Special Notes on Response Assessment

When nodal disease is included in the sum of target lesions and the nodes decrease to ‘normal’ size (< 10 mm), they may still have a measurement reported on scans. This measurement should be recorded even though the nodes are normal in order not to overstate progression should it be based on increase in size of the nodes. As noted earlier, this means that patients with CR may not have a total sum of ‘zero’ on the CRF.

Patients with a global deterioration of health status requiring discontinuation of treatment without objective evidence of disease progression at that time should be reported as ‘symptomatic deterioration’. Every effort should be made to document objective progression even after discontinuation of treatment. Symptomatic

deterioration is not a descriptor of an objective response: it is a reason for stopping study therapy.

Conditions that define ‘early progression, early death and inevaluability’ are study specific and should be clearly described in each protocol (depending on treatment duration, treatment periodicity).

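### The SAP gives no rule for non-RECIST clinical progression in PFS; where a site codes it as PD, imaging may stop and the patient can be censored because she progressed

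*SAP*

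**What the plan says.** **Event definition.** In SAP 6.1, PFS "is defined as the time from start of treatment to the date of documented progressive disease (PD) by RECIST v1.1 criteria" or death from any cause. Protocol 8.1.2 has PFS "defined as the period of time from the date of first infusion to the date of PD, death (due to any cause"; PD carries no RECIST qualifier there, and a patient with neither event is measured to her last tumor evaluation. Protocol 7.1 adds: "The date of response, the date of clinical or radiological PD, and the date of death will be registered". The SAP does not say what is done with a clinical PD date.

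**Censoring.** For an event after subsequent antitumor therapy, SAP 6.1 gives a rule for both PFS and DR, "in which case the patient will be censored at the time of last disease assessment prior to or on the first day of the first" such therapy. For PFS only, more than one missing follow-up before progression, death or further therapy also leads to censoring at the last valid assessment.

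**Assessment after stopping.** Protocol 6.7 lists a tumor assessment at the end-of-treatment visit, "if not previously done and if the reason for treatment discontinuation was other than PD". Protocol 6.8 gives follow-up assessments "only to those patients who discontinue treatment without documented disease progression". Footnotes 8 and 10 of the schedule of assessments follow the same pattern. Appendix 2, section 2.4.2, on patients who stop for global deterioration without objective progression, says: "Every effort should be made to document objective progression even after discontinuation of treatment".

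**Duration of response.** In the SAP, DR "is defined as time from first observation of response to the date of disease progression, recurrence or death. Other causes will be censored". Appendix 2, section 2.6.2, ends it when recurrence or progression is objectively documented.

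**The concern.** The SAP's event is RECIST progression, but the protocol rules that end imaging turn on PD or documented progression without that qualifier. A patient judged clinically to be progressing, and coded as PD, may therefore leave imaging before a RECIST event can be recorded. If she then starts another therapy, she is censored at her last assessment before that therapy, at which she had not progressed.

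The reason for her censoring is her progression. Kaplan-Meier assumes that censored patients have the same prospects as those still at risk, and here they plainly do not. The curve is pushed up. There is no concurrent arm in which the same bias could offset it. The same patient can also be an event under the protocol's definition and censored under the SAP's.

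**Working it through.** **No figure to reproduce.** The documents state no PFS target and no expected rate of clinical-only progression. The check follows one patient through the rules and then sizes the effect under stated assumptions.

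**The path through the rules.**
1. The investigator judges progression on clinical grounds; RECIST criteria are not met or not measured. Protocol 7.1 has the date recorded.
2. If the stop reason is coded as progressive disease, 6.7 no longer calls for the end-of-treatment assessment. If this also counts as documented progression, 6.8 no longer calls for follow-up assessments.
3. New antitumor therapy starts. SAP 6.1 censors her at her last assessment before it.
4. If instead she dies with no prior new therapy and no more than one missed follow-up, she remains an event.

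**Inputs from the documents.** Scans every six weeks to Cycle 6 (weeks 6, 12, 18), then every nine weeks (protocol 7.1). Kaplan-Meier estimation with PFS3 and PFS6 (SAP 6.2.2).

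**Assumptions not in the documents.** Exponential time to progression with median m = 3 or 4 months; a share f of progressions that is clinical only (5%, 10%, 20%); everyone in that share censored at the previous scan; no other losses. With 1 week = 12/52.18 months, weeks 12, 18 and 27 fall at 2.76, 4.14 and 6.21 months, so the 6-month reading lies after the third scan and before the fourth.

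**Formulas.** Let S(t) = 2^(−t/m), and let p be the chance of progressing in a six-week interval: p = 1 − 2^(−(4.14/3)/m).
- (a) Clinical PD is an event at its own date: PFS6 = (1 − f)·S(4.14) + f·S(6).
- (b) Clinical PD is censored at the previous scan. In each interval a fraction fp leaves the risk set and (1 − f)p are events among 1 − fp at risk, so the survival factor is (1 − p)/(1 − fp) and PFS6 = [(1 − p)/(1 − fp)]³.

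**Example, m = 3, f = 10%.** p = 0.273, S(4.14) = 0.384, S(6) = 0.250. (a) 0.9 × 0.384 + 0.1 × 0.250 = 0.371. (b) (0.727/0.9727)³ = 0.418. Difference 4.7 points.

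| Median | f | (a) event | (b) censored | Difference (points, before rounding) |
|---|---|---|---|---|
| 3 mo | 5% | 37.8% | 40.0% | 2.3 |
| 3 mo | 10% | 37.1% | 41.8% | 4.7 |
| 3 mo | 20% | 35.7% | 45.5% | 9.7 |
| 4 mo | 5% | 48.1% | 50.4% | 2.3 |
| 4 mo | 10% | 47.5% | 52.1% | 4.6 |
| 4 mo | 20% | 46.1% | 55.6% | 9.5 |

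A simulation of 200,000 patients per setting agrees to within 0.2 points. The same formulas at 3 months (two intervals, week 12) give PFS3 differences of about 1.5 to 7 points.

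**Two reductions.**
- *Prompt deaths.* If 30% of clinical-only progressors die a month later without new therapy and count as events, the simulated censored-rule PFS6 at m = 4 is 49.9%, 50.8% and 52.9%, against 48.1%, 47.4% and 46.2% with clinical PD as an event. The inflation is then 1.8, 3.4 and 6.7 points.
- *Choice of comparator.* Part of the difference arises because a clinical date precedes the next scan. Had imaging continued and shown PD at the next scan, PFS6 would be S(4.14), which is 38.4% (m = 3) or 48.8% (m = 4). Against that, the 20% row is inflated by 45.5 − 38.4 = 7.1 or 55.6 − 48.8 = 6.8 points.

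**The case against.** A RECIST-defined PFS event is a legitimate choice, and PFS is secondary in an exploratory trial. Several stronger readings that a reader might infer are not supported by the documents.

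- *That these patients get no further scans.* The protocol does not say so. Whether clinical progression counts as documented progression is left open. Section 6.2.1.1 asks for every effort to complete scheduled assessments, and Appendix 2, section 2.4.2, asks for objective progression to be sought. On that reading imaging continues. These passages do not settle the matter, because 6.7 and 6.8 can be read to schedule no tumor assessment for a patient stopped for PD.
- *That sites must code such patients as PD.* SAP Table 10.2.1 has no category for clinical progression, but it also offers investigator's decision and other, both itemised in Listing 10.2.2.
- *That clinical PD always means non-RECIST PD.* Appendix 2 accepts caliper measurement of superficial lesions, so some clinical PD is RECIST PD.
- *That later deaths drop out as a matter of course.* They do so only after new therapy or more than one missed follow-up. The SAP does not say whether an assessment no longer required counts as missed.
- *That DR is overstated too.* The SAP's end event for DR has no RECIST qualifier, and the missed-follow-up rule is stated for PFS only. Appendix 2, section 2.6.2, requires objective documentation, so the DR rule is ambiguous rather than shown to be biased.
- *That the full 10 points should be expected.* That figure needs a 20% share, with every such patient censored and none of their deaths counted.

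What stands against all this is that the SAP has no rule for a clinical PD date in PFS, and the assessment sections do not fit together.

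**Conclusion.** The concern holds for PFS, conditional on site coding. The SAP narrows the PFS event to RECIST progression, while the protocol's definition and its rules for ending imaging use unqualified PD. Where a site codes non-RECIST clinical progression as PD and new therapy follows, censoring is informative and PFS, PFS3 and PFS6 are biased upward.

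The direction is firm. The size rests on an assumed share that the documents do not give, and on an exponential model: about 2 to 10 PFS6 points for shares of 5% to 20%, or about 2 to 7 (4-month median) with 30% prompt deaths. ORR, the futility rules and the sample size are not touched. For DR, the finding is only that the SAP should say which progression definition applies.

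**What to change.** 1. In SAP 6.1, add a PFS sensitivity analysis in which non-RECIST clinical PD is an event at its recorded date, shown beside the RECIST-only analysis with PFS3 and PFS6.
2. Report how many patients were censored after clinical PD, so that a reader can judge whether the issue matters in the data.
3. State in SAP 6.1 which progression definition ends DR.
4. Reconcile protocol 6.7, 6.8 and schedule footnotes 8 and 10 with Appendix 2, section 2.4.2, on tumor assessment after non-RECIST progression.

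**Cost.** Items 1 to 3 need SAP wording, one derived variable and a little extra output. They use dates that protocol 7.1 already has registered, but confirm first that the data distinguish clinical from RECIST PD. Item 4 is a consistency request; its burden depends on how the sponsor resolves it, since keeping patients under 6.8 would mean repeated follow-up assessments. The other downside is a slightly less favourable PFS figure alongside the RECIST-only one.
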